Traditional measures of drug effect and medication side effects are often designed to be administered directly to participants. Given that THC-AD participants will have dementia and in many cases severe dementia, we propose to rate the following two questionnaires on the basis of “all evaluable data” including participant interview, chart review, and discussion with clinical staff.

- **Drug Effect Questionnaire (DEQ) (Appendix 2):** The subjective ratings of cannabis intoxication will be determined using the Drug Effect Questionnaire (DEQ). The individual items of the DEQ include ratings of drug effects (e.g. drug effect, pleasant effect, unpleasant effect) and behavioral/mood states often associated with cannabis intoxication (e.g. relaxed, paranoid, hungry/have munchies). Each item will be rated using a 100mm visual analog scale (VAS) anchored with “not at all” at one end and “extremely” at the other end. We have shown this method is sensitive to detecting dose effects of cannabis and dronabinol. There are few data reflecting the validity and reliability of the DEQ in persons with cognitive impairment, and most neuropsychiatric measures in this field require the use of an informant. [name], our substance abuse specialist and co-I, has developed an informant version of the DEQ (Appendix 2). The items are similar but worded to be administered to an informant.
- **Medication Side-Effects Questionnaire:** Research staff will interview participants and clinical staff and will rate on a 4-point scale (none, mild, moderate, strong) their impression of potential side effects of dronabinol. Based on the list of potential side effects from clinical trials with dronabinol, items will include nausea, diarrhea, dry mouth, upset stomach, vomiting, vivid or abnormal dreams, anxiety, dizziness, fatigue, confusion, depersonalization, hallucination, paranoia, depression, rapid heart rate/palpitations, flushing in the face or body, tinnitus, speech difficulty, blurred vision, headache, sweating, runny nose, and coughing.

Safety and Adverse Event (AE) monitoring

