All AEs occurring after randomization and during the 3-week treatment period, regardless of adherence to study treatment, will be recorded at all contacts. AEs will be assessed by using all available data to determine if new symptoms or medical events have occurred. A list of common side effects of dronabinol will be used to monitor for adverse events. At scheduled visits, participants and clinical staff/family caregivers will be interviewed about whether the participant experienced any symptoms or side effects on the list since the last visit. Adverse events, other than what is listed as common side effects, will still be recorded. If adverse events are noted, they will be rated as mild, moderate, or severe based on their clinical severity and frequency. Finally, medical transfers to outside general hospitals (McLean) or to a medical/surgical unit in the same hospital (Johns Hopkins and Miami Jewish Health) will be monitored. The PIs and designated study physicians will be responsible for monitoring the safety of participants. They will be responsible for appropriate medical care of participants during the study in connection with

Protocol: Pilot trial of dronabinol adjunctive treatment of agitation in Alzheimer's disease (AD) (THC-AD)
Protocol Number: IRB00052955 **Protocol Version:** 6.0/2July2020

study procedures. Safety assessments will include physical exams, vital signs, ECGs, monitoring of adverse events, and monitoring and maintenance of concurrent medication records. AEs will be reported to the local IRBs per local policy. Serious adverse events (SAEs) will be defined per FDA guidelines and reported in a timely manner as is standard in clinical trials (with the initial report being next business day). In addition, we will add the following DSMB-agreed upon SAEs to the SAE definition:

- 1) Death (already defined as an SAE per standard FDA guidelines)
- 2) Delirium at two consecutive weekly assessments
- 3) Seizures
- 4) Fall resulting in injury

In accordance to FDA reporting requirements, any serious adverse events (SAEs) that occur at Johns Hopkins, Miami Jewish Health, and McLean Hospital will be reported to Johns Hopkins and [name], M.D., the Sponsor-Investigator. Expected SAEs include delirium, intoxication, sedation, and increased appetite. Such reporting will adhere to the following process:

- 1) Sponsor-Investigator will be notified of the SAE and will be given a report

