Medical History	X				
Other Medications	X				
Randomization		X			
Study medication dispensing		X	X	X	
Coronavirus Impact Scale (CIS)		X			
Unblinding*					X *
Clinical Instruments					
Pittsburgh Agitation Scale (PAS)		X	X	X	X
Neuropsychiatric Inventory, Clinician Version (NPI-C)		X	X	X	X
Cohen-Mansfield Agitation Inventory (CMAI)		X	X	X	X
Modified Alzheimer's Disease Cooperative Study- Clinical Global Impression of Change (CGI-C)		X	X	X	X
Alzheimer's Disease Cooperative Study - Activities of Daily Living (ADCS-ADL)		X	X	X	X
Confusion Assessment Method (CAM)		X	X	X	X
Sleep Assessment (NPI-C Sleep Subscale)		X	X	X	X
Cognition					
SIB-8		X			X
Mini Mental State Exam (MMSE)		X			X
Drug Effect					
Drug Effect Questionnaire (DEQ)		X	X	X	X
Medication Side-Effects Questionnaire		X	X	X	X
Safety and AE monitoring					
Physical Exam	X				
Neurological Exam	X				
Vital Signs		X	X	X	X
General Medical Health Rating (GMHR)	X				
Adverse Event Monitoring		X	X	X	X
ECG		X			X
Blood draw (DNA, Biomarker, CBC, CMP, TSH)		X			X

*Only done after all other study procedures are complete

Protocol: Pilot trial of dronabinol adjunctive treatment of agitation in Alzheimer's disease (AD) (THC-AD)

Protocol Number: IRB00052955

Protocol Version: 6.0/2July2020

6. **Biostatistical Analysis:**

All analyses will be conducted using STATA (55) and R (56) under the supervision of the study statistician ([name]). Descriptive analyses will be conducted and measures checked for outliers and to ensure that distributional assumptions of the planned analyses are appropriate. If not, analogous non-parametric methods will be used. Analyses will be intent-to-treat. We expect minimal missing data, but if there is a significant amount of missing data, multiple imputation may be used if appropriate (57). To investigate sensitivity to missing values, those with and without missing values will be compared by background covariates. Tests will be two-sided and p-values <0.05 will be considered significant.

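### Adverse events are judged without reference to the Baseline level, so counts by event type may miss worsening or take in unchanged symptoms

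*Combined protocol and SAP*

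**What the plan says.** Three statements in Section 5 of the protocol bear on what counts as an AE.

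- **The rule.** Under Safety and Adverse Event (AE) monitoring, "AEs will be assessed by using all available data to determine if new symptoms or medical events have occurred". The list of safety assessments that closes the subsection repeats it. Neither place mentions worsening of a symptom that was already present.
- **The interview.** At scheduled visits, participants and staff or family caregivers are "interviewed about whether the participant experienced any symptoms or side effects on the list since the last visit". This is not limited to new symptoms.
- **The grading.** When AEs are noted, "they will be rated as mild, moderate, or severe based on their clinical severity and frequency". No pre-treatment reference is given.

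Under Drug effect monitoring, research staff complete the Medication Side-Effects Questionnaire, on which they "will rate on a 4-point scale (none, mild, moderate, strong) their impression of potential side effects of dronabinol". Its items include "confusion, depersonalization, hallucination, paranoia, depression". Tables 1 and 2 both schedule it at Baseline and at Weeks 1, 2 and 3.

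Section 6 (Biostatistical Analysis), Aim 2, models the risk of a severe AE and the total AE count by arm. It then examines each AE type by arm, to identify events that a larger trial should be powered to detect. Section 6 does not name the questionnaire and states no rule for treatment-emergent events.

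**The concern.** All participants have dementia, often severe, so some confusion before the first capsule is to be expected. For a symptom that is already present, the two rules give opposite answers, and neither isolates the change that treatment might have caused. If 'new' is taken literally, a participant who goes from mild to strong confusion has no AE. If any listed symptom counts, a participant whose confusion never changes has one, on either arm.

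Both errors shrink the difference between arms. That matters because Hypothesis 2 predicts AEs not significantly different from placebo, so dilution favours the hypothesis. It also matters because the counts by type are meant to guide the safety endpoints of a later trial. Aim 2 further compares AE rates across sites and for outpatients. If sites resolve the ambiguity differently, some of those differences would reflect the rule and not the patients.

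**Working it through.** The plan states no figure for the safety aim, so there is none to reproduce. The check has three parts.

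**1. One symptom under each rule**

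| Baseline to worst later rating | 'New symptom' | 'Any listed symptom' | Change from Baseline |
|---|---|---|---|
| none to moderate | AE | AE | AE |
| mild to strong | no AE | AE | AE |
| moderate to moderate | no AE | AE | no AE |

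The rules agree only for a participant who starts without the symptom.

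**2. Size of the dilution (illustration)**

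Inputs from the protocol: 80 randomized (Section 3) at close to 1:1 (Randomization and blinding), hence about 40 per arm; two-sided 0.05 (Section 6).

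Assumed, because the documents give no values:
- p, the share with the symptom at Baseline;
- r, the true rate of onset or worsening in each arm, taken as unrelated to Baseline status;
- Baseline symptoms persist and are reported at later visits.

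Expected rate in an arm:
- change from Baseline: r
- 'new symptom': r(1 − p)
- 'any listed symptom': p + r(1 − p)

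Under both of the last two, the difference between arms is (r_drug − r_placebo)(1 − p). For a 20-point excess:
- p = 20%: 20 × 0.8 = 16 points
- p = 40%: 20 × 0.6 = 12 points
- p = 60%: 20 × 0.4 = 8 points
- p = 80%: 20 × 0.2 = 4 points

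Power uses the normal approximation for two proportions, Φ[(d − 1.96·se0)/se1], with se0 pooled and se1 unpooled. Example for 'new symptom', r = 10% vs 30%, p = 50%: rates 5% and 15%, d = 0.10, se0 = √(0.10 × 0.90 × 2/40) = 0.0671, se1 = √[(0.05 × 0.95 + 0.15 × 0.85)/40] = 0.0661, so Φ(−0.48) = 0.32.

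For r = 10% vs 30%, power under the change rule is 0.61 at every p. Under the other two:

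| p | 'New': placebo, drug | Power | 'Any listed': placebo, drug | Power |
|---|---|---|---|---|
| 25% | 7.5%, 22.5% | 0.47 | 32.5%, 47.5% | 0.28 |
| 50% | 5%, 15% | 0.32 | 55%, 65% | 0.15 |
| 75% | 2.5%, 7.5% | 0.17 | 77.5%, 82.5% | 0.08 |

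Under 'new', the uncounted worsenings on drug are 40 × 0.30 × p = 3, 6 and 9; on placebo, 40 × 0.10 × p = 1, 2 and 3.

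Other assumed rates, with p = 25, 50 and 75%:
- 10% vs 40%: change 0.89; 'new' 0.74, 0.53, 0.28; 'any listed' 0.53, 0.28, 0.13.
- 5% vs 20%: change 0.53; 'new' 0.41, 0.28, 0.16; 'any listed' 0.18, 0.10, 0.06.

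The 'any listed' reading loses more power throughout: the difference is equally small, and background symptoms add variance.

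**3. What other measures cover**

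| Symptom | Other measure named in the plan | Limit |
|---|---|---|
| Confusion | SIB-8 (Aim 2), MMSE (secondary) | Baseline and Week 3 only |
| Confusion | CAM, weekly | identifies delirium, not graded worsening below it |
| Paranoia | 'paranoid' item of the DEQ, weekly | protocol notes few validity data in cognitive impairment |
| Hallucination | none named in Section 6 | – |

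None of these measures is said to feed the AE counts.

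**The case against.** A reader might infer that drug-induced worsening is simply not counted as harm. The documents do not support that. The interview elicits any listed symptom, the AE rule draws on all available data, and a worsening graded severe could enter the severe-AE model. Cognition is assessed mainly as a safety measure, Baseline delirium is an exclusion, and CAM is repeated weekly. What stands is that the text is ambiguous and that neither reading compares with Baseline.

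A reader might also compare "Expected SAEs include delirium, intoxication, sedation, and increased appetite" with the questionnaire items and infer that such events would be lost. That mostly fails. The DEQ rates intoxication and hunger, and its change is modelled. Seizures and falls with injury are SAEs by agreement with the DSMB. AEs not on the list are still recorded. The protocol also does not say that the list used for AE monitoring is the questionnaire's list. Sedation has no close counterpart, but fatigue is listed.

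Three further points deserve weight.
- The questionnaire records raters' impressions of possible drug side effects, not bare symptom presence, so one cannot assert that background symptoms would dominate the counts.
- The list of secondary outcomes in Section 6 is open-ended, so the questionnaire might be analysed. Nothing commits the team to it, though.
- Counts by type are a supplementary part of Aim 2, after severe AEs and total counts. They are still the part meant to inform the next trial.

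**Conclusion.** The point holds as a defect in the AE rule and an omission in the analysis. Worsening of a pre-existing symptom may go uncounted, or unchanged symptoms may be counted in both arms; each dilutes the Aim 2 counts by AE type. Confusion and paranoia are partly covered elsewhere. Hallucination is the clearest gap.

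The size cannot be fixed from the documents. The range of 16 to 4 points for a true 20-point excess rests on assumed prevalences of 20 to 80% and on worsening being unrelated to Baseline status. If most drug effects were new onsets in people free of the symptom, the 'new' rule would lose less; if they fell mainly on those already affected, it would lose more. Pre-existing confusion is a reasonable expectation here, but the documents give no baseline rates for hallucination or paranoia. The plan should be changed because the ratings needed are already scheduled.

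**What to change.** 1. In both places in Section 5 where the AE rule appears, replace new symptoms with new symptoms or worsening from Baseline, and state that an unchanged Baseline symptom is not an AE.
2. In Section 6, Aim 2, name the Medication Side-Effects Questionnaire and report, by arm, the worst post-baseline change from the Baseline rating on each item.
3. State in advance how large a rise counts as worsening. One category on the 4-point scale is an option, but the documents give no reliability data for the scale. The table in item 2 shows the full distribution and does not depend on that choice.

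The cost is wording in two places, one more safety table and somewhat more mild AEs in both arms. No visit or instrument is added. Version 6.0 and a remark in Section 6 about participants not having been stopped suggest that enrolment had begun. If so, apply the Baseline-referenced rule to all participants from the questionnaire ratings already collected, so that two ascertainment rules are not mixed. No new questionnaire items for intoxication, appetite, seizure or falls are requested.

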
Protocol: Pilot trial of dronabinol adjunctive treatment of agitation in Alzheimer's disease (AD) (THC-AD)

Protocol Number: IRB00052955

Protocol Version: 6.0/2July2020

There is a great need for better interventions that target Agit-AD, a major source of patient disability as well as caregiver burden and stress, particularly in the case of moderate to severe agitation. This pilot trial could open the door to “repurposing” dronabinol as a novel and safe treatment for Agit-AD with significant public health impact.

2. Specific Aims:

We propose THC-AD: a three-week placebo-controlled, double-blind, randomized clinical trial of dronabinol (10 mg QD) in 80 patients with severe Agit-AD. Concomitant medications will be limited to currently used antipsychotics, antidepressants, benzodiazepines, as well as anticonvulsant therapy when not used for seizure disorder, with lorazepam 0.75 QD total daily allowed as rescue medication, and can be administered orally or intramuscularly. Additionally, these four categories of currently used concomitant medications are permitted to be used with PRN trazodone in doses up to 100 mg total daily dose for agitation and insomnia.

AIM 1: To compare the efficacy of three weeks of dronabinol adjunctive treatment to placebo in 80 patients with severe Agit-AD.

Hypothesis 1: Compared to placebo, dronabinol treatment will be associated with a greater reduction in symptoms of agitation as measured by co-primary outcomes of a) PAS b) NPI-C Agitation, Aggression, and the sum of Agitation and Aggression. The Cohen-Mansfield Agitation Inventory will be a secondary agitation outcome. Psychosocial function, cognition, and sleep will be assessed for potential benefit.

AIM 2: To compare the safety of three weeks of dronabinol adjunctive treatment to placebo in 80 patients with severe Agit-AD.

Hypothesis 2: Dronabinol treatment will be well tolerated with (AEs) not significantly different than placebo, including incident delirium as measured by the Confusion Assessment Method (CAM).

Outcomes:

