clinical and research settings to monitor symptoms of agitation that may fluctuate during the course of a day or week and to assess the response to therapeutic interventions. The PAS rates the severity of agitation in four behavioral domains: Aberrant Vocalization, Motor Agitation, Aggressiveness, and Resisting Care, on a scale ranging from 0 to 4. Anchor points guide the rater to assign the highest possible score within each behavior group so that the score reflects the most aberrant behavior during a period of observation. The PAS takes less than 1 minute to complete. Reliability and validity were assessed in an acute-care psychogeriatric unit and a chronic-care nursing facility. The intra-class correlation for four nurses using the PAS during their work on the inpatient unit was +0.82 for the PAS Total Score.

- **Neuropsychiatric Inventory, Clinician Version (NPI-C) (41)** (Co-Primary Outcome) The NPI-C is an improved version of the Neuropsychiatric Inventory (NPI) (42) that has been expanded to have separate subscales for “Agitation” and “Aggression”. We will use clinically significant NPI-C Agitation or Aggression as entry criteria for the study and as co-primary outcomes. There is a training DVD available for the NPI-C. The validation study (41) not only reported good inter-rater reliability but better convergent validity than the NPI with other agitation instruments such as the Cohen-Mansfield Agitation Inventory (CMAI). We propose to use NPI-C Agitation, Aggression, and the sum of Agitation and Aggression as co-primary outcomes.
- **Sleep assessment (NPI-C Sleep Subscale):** Sleep is an important outcome in on its own and additionally may be associated with Agit-AD. Sleep will be quantified by using the Sleep Disorders subdomain of the NPI-C. The NPI-C collects information on eight domains of sleep quality and behavior. Information is collected on frequency and severity of sleep problems that patients commonly experience. We will use the NPI-C Sleep Disorders subdomain score as a secondary outcome.
- **Alzheimer’s Disease Cooperative Study – Activities of Daily Living (ADCS-ADL):** a 27-item instrument assessing participant’s ability to perform activities of daily living (ADLs) (43). THC-AD staff will assess the ADCS-ADL by chart review and, where necessary, interview clinical staff who interact daily with the participant. The ADCS-ADL has been used to assess ADLs as an outcome measure in clinical trials targeting moderate-to-severe dementia (44)

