Multiple test corrections will be applied as appropriate. All primary analyses will be adjusted for site as well as the variables balanced through minimization (use of antidepressants and use of antipsychotics). To account for the inclusion of multiple sites, we will include site as a covariate, with individuals being seen on an outpatient (largely remote) basis being treated as its own site. Secondarily, we will fit models with site, site x time, and site x treatment x time to determine if there are any effects of site on treatment effect over time. These analyses must be secondary as the study was not powered to detect these 3 way interactions. Importantly, no participants were stopped during their participation and all participants will have the same mode of assessment (either in-person or remote) throughout.

Aim 1: Efficacy will be assessed by fitting a longitudinal linear model with the co-primary outcomes (PAS and NPI-C Agitation/Aggression/Sum of Agitation and Aggression) and with time, treatment assignment and interaction between time and treatment. The latter term will be the coefficient of interest and will represent the mean difference in change over the 3-week period between the treated and placebo groups. Within-person correlations will be handled via the method of generalized estimating equations (58).

Aim 2: We will model risk of a severe adverse event as a function of treatment assignment using logistic regression, and counts of total adverse events using ordinal logistic regression or poisson regression as appropriate. We will also scrutinize counts of each specific type of AE as a function of treatment assignment to determine if there are specific adverse events which we should power ourselves to detect in future larger-scale trials. Special attention will be paid to new-onset delirium, seizures, and arrhythmias. Additionally we will specifically look at the effect of dronabinol on cognition using the SIB-8, and a regression model analogous to that in Aim 1. We will stratify adverse events by site and assess whether rates of particular AEs vary by site. In particular, we will assess whether outpatients differ in their rates and types of AEs (either favorably, due to being less acute, or unfavorably, due to a less controlled environment where falls might be more likely, for example).

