Secondary Analyses: We will model change in additional outcomes (e.g., CMAI, MMSE, sleep, DEQ) using models analogous to that of Aim 1. We will also look at predictors of dronabinol response, including cannabinoid receptor polymorphisms and other patient characteristics. We will also model change in IL1 β , TNF α , and IL6 as a function of treatment assignment. All secondary analyses will be conducted with site as a covariate, and additional analyses which include site x treatment and site x treatment by time will be performed.

Sample size and Power analysis

Protocol: Pilot trial of dronabinol adjunctive treatment of agitation in Alzheimer's disease (AD) (THC-AD)

Protocol Number: IRB00052955

Protocol Version: 6.0/2July2020

We observed a large effect in our observational study that used PAS as outcome. PAS is one of the co-primary outcomes and we will estimate power to detect change in PAS. There are no pilot data to estimate power to detect change in NPI-C which has not been used in prior trials of dronabinol. The PAS declined in our observational study from 9.68 (3.91) pre-treatment to 5.25 (4.17) post-treatment for a treatment effect of 1.1 and 45% reduction in PAS score.

We propose to use a more conservative estimate of 30% reduction in PAS score and calculated statistical power using the formulae of Jung and Ahn (59). A 30% reduction translates to decreasing from 9.68 PAS points to 7.26 points after 3 weeks, which means a slope of -0.81 points/week. This translates to an effect size of 0.206. It is essential to account for missing data including those from dropouts. Assuming first a missing data pattern that increases monotonically to 15% by week 3, with N= 80, a within-person correlation of 0.5 and an exchangeable correlation structure, we will have 80% power to detect a treatment effect of size 0.22, which translates to a decrease in PAS from 9.68 to 7.1 over 3 weeks; this is a 26.7% decrease. Assuming next a missing data pattern that increases monotonically to 30% by week 3, then with 80 people and a within-person correlation of 0.5 and an exchangeable correlation structure, we would have 80% power to detect a treatment effect of size 0.24, which translates to a decrease in PAS from 9.68 to 6.87 over 3 weeks; this is a 29.1% decrease. Thus, THC-AD is well-powered to detect a clinically plausible and conservatively estimate decrease in PAS which is a co-primary outcome.

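### The plan lists four co-primary scores but sets no test family, order or success rule, and its 80% PAS power holds only under some of the rules left open

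*Combined protocol and SAP*

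**What the plan says.** Three places call four scores co-primary. Hypothesis 1 in section 2 (Specific Aims) refers to "co-primary outcomes of a) PAS b) NPI-C Agitation, Aggression, and the sum of Agitation and Aggression". The NPI-C entry under Clinical Assessments in section 5 says "We propose to use NPI-C Agitation, Aggression, and the sum of Agitation and Aggression as co-primary outcomes". Section 6, Aim 1, describes "fitting a longitudinal linear model with the co-primary outcomes (PAS and NPI-C Agitation/Aggression/Sum of Agitation and Aggression". The Outcomes text in section 2 instead counts two primary measures, PAS and NPI-C, so the family could be read as two instruments or four scores.

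Section 6 sets the significance level, "Tests will be two-sided and p-values <0.05 will be considered significant", and then says "Multiple test corrections will be applied as appropriate". The documents do not say which tests form the family, which correction is used, in what order scores are tested, or whether success needs one, some or all of them.

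The Sample size and Power analysis text is open about its scope: "PAS is one of the co-primary outcomes and we will estimate power to detect change in PAS" and "There are no pilot data to estimate power to detect change in NPI-C". For N=80 with 15% missing by week 3 it states "we will have 80% power to detect a treatment effect of size 0.22". It gives matching figures of 0.24 (N=80, 30% missing), 0.25 (N=60, 15%) and 0.27 (N=60, 30%), and concludes that power for PAS is good.

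**The concern.** Several co-primary scores and one nominal 0.05 level leave the meaning of a positive trial open. The common rules behave differently:

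- **Any score may win, uncorrected:** false-positive risk exceeds 5%.
- **Alpha is shared:** 5% is kept, but PAS no longer has the stated power.
- **All scores must win:** 5% is kept and PAS has its stated power, but the chance that the whole trial succeeds is below 80%.
- **PAS is tested first at full alpha:** both 5% error and the stated PAS power hold.

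The plan does not choose. If PAS and NPI-C disagree, the rule could be settled after the results are known. That possibility is practical here: under section 9 the trial's own statisticians supply unblinded data to the DSMB, and under Unmasking in section 4 each participant is unmasked at their endpoint.

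**Working it through.** **Inputs from the plan.** N=80 or 60; allocation close to 1:1; PAS at weeks 0, 1, 2 and 3; exchangeable within-person correlation 0.5; missingness rising monotonically to 15% or 30% by week 3; the GEE slope-comparison formula of Jung and Ahn; baseline PAS 9.68, SD 3.91. Effects are in SD per week. **Assumption:** missingness builds up linearly (0/5/10/15% or 0/10/20/30%), since the plan gives only the week-3 value.

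**Step 1: reproduce the stated power.** Let p(j) be the proportion observed at week t(j), τ the p-weighted mean week, S = Σ p(j)(t(j) − τ)², and C = Σ over j≠k of 0.5 × p(jk)(t(j) − τ)(t(k) − τ). With monotone dropout, p(jk) is the proportion observed at the later week. In SD units:

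Var(slope difference) = (S + C) / (N × 0.25 × S²); power = Φ(effect/SE − z), where z is the two-sided critical value.

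For N=80 and 15% missing: τ = 5.30/3.70 = 1.432, S = 4.608, C = −2.093. Var = 2.515/(20 × 21.235) = 0.00592, so SE = 0.0770. At two-sided 0.05, 0.22/0.0770 − 1.960 = 0.899 and Φ(0.899) = 81.6%. For 30% missing: S = 4.176, C = −1.674, SE = 0.0847. For N=60 the SEs are multiplied by √(80/60), giving 0.0889 and 0.0978.

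| N, missing | Stated effect | Power, alpha 0.05 | Power, 0.025 | Power, 0.0125 |
|---|---|---|---|---|
| 80, 15% | 0.22 | 81.6% | 73.1% | 64.1% |
| 80, 30% | 0.24 | 80.9% | 72.3% | 63.2% |
| 60, 15% | 0.25 | 80.3% | 71.6% | 62.4% |
| 60, 30% | 0.27 | 78.8% | 69.8% | 60.4% |

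The stated 80% matches the 0.05 column. One-sided 0.05 gives 87% to 89% and does not fit, nor do the two smaller alphas. The power section does not restate alpha; the general two-sided 0.05 plus this match shows that no correction was built in.

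**Step 2: effects detectable with 80% power.** Effect = (z + 0.842) × SE. Going from 0.05 to 0.025 multiplies it by (2.241 + 0.842)/(1.960 + 0.842) = 1.10.

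| N, missing | Alpha 0.05 | Alpha 0.025 |
|---|---|---|
| 80, 15% | 0.216 | 0.237 |
| 80, 30% | 0.237 | 0.261 |
| 60, 15% | 0.249 | 0.274 |
| 60, 30% | 0.274 | 0.302 |

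**Step 3: convert to PAS as the plan does.** Percentage decrease = effect × 3 weeks × 3.91/9.68. The plan's rounded effects give 0.22 → 26.7%, 0.24 → 29.1%, 0.25 → 30.3% and 0.27 → 32.7% (printed as 33%). Rounding the alpha-0.025 effects in the same way gives 0.24 → 29.1%, 0.26 → 31.5%, 0.27 → 32.7% and 0.30 → 36.4%.

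**Step 4: what the other rules would do.** These figures rest on assumed correlations, because the plan gives none for NPI-C.

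- Any one of four wins, uncorrected, no true effect: four independent tests would give 1 − 0.95⁴ = 18.5%. Because one score is the sum of two others, simulation gives about 11% to 16% (PAS–subscale and subscale–subscale correlations from 0.7 down to 0, subscales with equal SD).
- All four must win: if PAS and both subscales each have 80% power, joint power is about 51% to 66% over the same correlations.
- Disagreement: if PAS and the NPI-C sum each have 80% power, exactly one reaches p<0.05 in about 14% to 29% of trials (correlation 0.8 down to 0.2).

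**The case against.** The best defence has four parts.

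**Correction is promised.** This stands. A reader might infer that the plan tests four scores at 0.05 uncorrected and so runs an error rate of 11% to 16%. The documents do not support that; they commit to correction and leave its form open.

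**The power claim is candid.** The plan limits it to PAS and explains why NPI-C power was not calculated. This also stands. A reader might infer that the 80% is wrong or the trial underpowered. That does not follow: PAS keeps the stated power under a PAS-first order, and PAS taken alone keeps it if all scores must win. Even with shared alpha the loss can be small. Under Hochberg on PAS and the NPI-C sum, with 80% power for each and correlation 0.2 to 0.8, PAS power is 77% to 78%. It is 71% to 72% if NPI-C shows no effect.

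**The family may be two, not four.** The Outcomes text supports that reading, so the 60% to 64% at alpha 0.0125 should not be taken as the plan's power. It is a worst-case bound: the family size is unsettled and one score is the sum of two others.

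**It is a pilot.** This limits the weight of the point but does not remove it. The plan states an efficacy hypothesis, tests it at 0.05 and relies on a formal power claim.

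After all four, the family, order and success rule remain undefined.

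**Conclusion.** The concern holds as under-specification that affects the stated power, and it should be corrected. The documents do not settle whether there are two or four primary tests, how they are corrected, or what counts as success. The 80% is that of one PAS test at an uncorrected two-sided 0.05. It holds under some of the open rules and drops to about 70% to 73% in the worst case with two tests. Those PAS figures rest on the plan's inputs plus linear build-up of missingness. The error rate for an uncorrected any-win rule, the joint power and the disagreement rates also depend on assumed correlations, and the last two on assumed NPI-C power; with no NPI-C pilot data in the plan they are illustrative only.

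**What to change.** Adopt one rule by dated amendment, decided by people who have not seen efficacy results by arm. The choice is the sponsor's.

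**Option A: fixed order.** Test PAS first at two-sided 0.05. Only if it succeeds, test the NPI-C sum, then Agitation, then Aggression, each at 0.05, stopping at the first failure. This holds family-wise error at 5%, keeps the stated PAS power and retains all four scores. The cost is that nothing can be claimed on NPI-C if PAS fails.

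**Option B: shared alpha.** Test PAS and the NPI-C sum by Holm or Hochberg at overall two-sided 0.05, with success on either, and make the two subscales secondary. Restate the effects detectable with 80% power at the worst-case alpha of 0.025:

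| N, missing | Effect now stated | Restated effect | PAS decrease now stated | Restated decrease |
|---|---|---|---|---|
| 80, 15% | 0.22 | 0.24 | 26.7% | 29.1% |
| 80, 30% | 0.24 | 0.26 | 29.1% | 31.5% |
| 60, 15% | 0.25 | 0.27 | 30.3% | 32.7% |
| 60, 30% | 0.27 | 0.30 | 33% | 36.4% |

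The cost is a detectable PAS effect about 10% larger in the worst case before rounding, and the demotion of the subscales.

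Under either option, bring Hypothesis 1 and the Outcomes text in section 2, the NPI-C entry in section 5, and Aim 1, the multiplicity sentence and the power analysis in section 6 into line with the chosen rule. Neither option needs extra enrolment or new data.
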